## Study Overview

Study Overview	
Subjects	Recruit 60 subjects. Each subject will make 1-2 visits. The entire study is estimated to take approximately 6 months.
Inclusion/Exclusion Criteria	
Potential subjects will be given a checklist of the inclusion and exclusion criteria to determine if they are eligible to participate. A study staff will confirm the eligibility by the "yes" and "no" responses accordingly.
 
Inclusion Criteria (All answers should be yes):
 
 
• Between the ages of 5-17
 
• In good general health
 
• Fluent in English
 
• Parent or guardian willing and able to provide written informed consent
 
• Have 16 scorable teeth (non crown/bridge/or full amalgams)
 
• Have had a dental cleaning and exam in the past 24 months
 
 
Exclusion Criteria (To qualify, all answers must be no):
 
 
• Have advanced periodontal disease or severe gum disease
 
• Have mouth or teeth pain that prevents brushing in any areas
 
• Have intraoral piercings (tongue or lip) that cannot be removed
 
• Have non-controlled diabetes
 
• Have any autoimmune or infectious disease or any medical condition that would delay wound healing
 
• Have untreated visible cavities or untreated dental work
 
• Had oral or gum surgery in the previous 2 months
 
• Take antibiotic premedication for dental procedures
 
• Undergoing or require extensive dental or orthodontic treatment
 
• Current smoker
 
• Generalized recession over 1mm
 

Study Objectives	To compare plaque removal efficacy of an automated mouthpiece-based toothbrush to a manual toothbrush, and to assess effect on oral soft tissues.
Study Design	
 
• Single Site
 
• Parallel Design
 
• 60 Subjects stratified by dentition (primary, mixed, and permanent) are randomized evenly to 2 treatment groups
 
• Randomized, blinded, 2 treatment groups
 

Study Duration	
 
• 2 visits
 
• Each study visit will take approximately 90 minutes
 

Study Devices	
List of Devices:
 
Primary Investigation: (All 60 subjects)
 
 
1. Automated brush: 30 subjects
 
2. Manual toothbrush: 30 subjects
 

Study Summary	
Visit 1: Screening (may be by telephone)
 
 
• Inclusion / Exclusion reviewed
 
• Consent if in person visit
 
• Subject will be asked to abstain from brushing, flossing, gum or mouthwash for 24 hours prior to visit 2
 
• Schedule next visit
 
 
Visit 2:
 
 
• Consent
 
• Review Inclusion / Exclusion Questionnaire
 
• Randomization to experimental or control group
 
• Intraoral Evaluation by dental examiner
 
• Plaque disclosing and plaque score
 
• Intraoral photographs: (1 anterior, one posterior right and one posterior left)
 
• Brushing instructions
 
• Supervised and Timed Brushing with assigned product and measured toothpaste
 
• Restain with plaque disclosing solution and 2nd plaque index as well as gingival abrasion
 
• Intraoral photographs (1 anterior, one posterior right and one posterior left)
 
• Subject questionnaire
 

----------------------	--

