### **Duration of subject participation and duration of study:**

All subjects will have two visits and should complete the study in approximately two weeks. The visits may be combined following a telephone screening. Each appointment will be approximately 90 minutes.

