### **Schedule of Events:**

Procedures	Performed by:	Visit 1	Visit 2
Informed Consent	Research Staff	X	
Inclusion/Exclusion Criteria/Review	Research Staff	X	X
Enrollment	Research Staff	X	
Intra oral Examination	Examiner	X	
Randomization	Research Staff		X
Intra oral Examination (Pre & Post)	Examiner		X
Intra-oral photographs (Pre & Post)	Research Staff		X
Plaque disclosing index (Pre & Post)	Examiner		X
Brushing Dispense & Instruction	Research Staff		X

---

Study Product Usage	Subject		X
Schedule Next Study Visit	Research Staff	X	
Subject Compensation	Research Staff	X	X

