### **Selection and Withdrawal of Subjects:**

Potential subjects will be recruited via flyers or direct contact at the Center for Pediatric Dentistry, with a phone number to call. A study staff will go over a checklist of the inclusion and exclusion criteria to determine if they are eligible to participate. At the initial visit a dental examiner will confirm the eligibility by the “yes” and “no” responses accordingly and ask additional questions as appropriate. Subjects who sign the informed consent form are screened for eligibility at the baseline visit. Subjects meeting all eligibility criteria shall begin the study procedures.

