## **Subjects Study Visits**

### **Welcome Subject and Consent**

A research staff member who is currently trained in human subjects will greet the subject, and complete an eligibility inclusion/ exclusion form, and perform the consent process. Potential subjects are given the IRB-approved consent form to read and are provided the opportunity to ask questions about the study.

If any subject does not meet the requirement, they will not be screened further and will be thanked for their time.

If the potential subject does meet the requirement, study procedures may begin.

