### **Visit 2:**

- Review Inclusion / Exclusion Questionnaire
- Randomization
- Pre-brushing Intraoral Evaluation and plaque index
- Intraoral photographs pre-brushing
- Verbal review of brushing instructions
- Supervised and Timed Brushing with assigned products
- Dental examiner performs post- brushing intraoral evaluation and plaque index
- Intraoral photographs post-brushing
- Subject questionnaire
- Gift card dispensed

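### The Study Summary allocates a telephone-screened child before the examination that settles eligibility and could supply the dentition stratum, and both Visit 2 lists score baseline plaque after allocation

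*Protocol*

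**What the plan says.** **Order at Visit 2.** The Study Summary lists consent, questionnaire review, "Randomization to experimental or control group", the examiner's intraoral evaluation, and then plaque disclosing and scoring. The body list (Visit 2) runs the same way: questionnaire review, randomisation, then "Pre-brushing Intraoral Evaluation and plaque index".

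**Visit 1.** The Study Summary heads it "Visit 1: Screening (may be by telephone" and lists no examination on any route. It takes "Consent if in person visit" and lists consent again at Visit 2, so telephone-screened children are covered for consent. The body list for Visit 1 and the Schedule of Events do include an examiner's evaluation at Visit 1. The Schedule also has a second one at Visit 2, "Intra oral Examination (Pre & Post", and randomisation at Visit 2 only.

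**Combining visits.** The duration section says "The visits may be combined following a telephone screening". The body heading for Visit 1 also allows combination if the child has abstained from oral hygiene for 24 hours. Neither gives an order for the merged steps.

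**Eligibility.** Selection and Withdrawal of Subjects has a dental examiner confirm eligibility at the initial visit, and then "Subjects meeting all eligibility criteria shall begin the study procedures". Welcome Subject and Consent says "If any subject does not meet the requirement, they will not be screened further and will be thanked for their time". The Study Visits section makes the intraoral evaluation decisive for eligibility and times it before in-mouth use of the test product.

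**Stratification and blinding.** The Study Overview stratifies randomisation by dentition in three classes. The SAP says dentition was recorded at clinical examination. The protocol calls the trial single-blinded without saying who is blinded.

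**The concern.** Several entry criteria need someone to look in the mouth: the count of scorable teeth, untreated visible cavities, generalised recession. A telephone questionnaire cannot settle them. If the Study Summary is followed as listed, a child screened by telephone receives an arm before anyone has looked. Three things are then at stake.

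- A child found ineligible at the examination is lost after allocation.
- The examined dentition class is not available to the person using the randomisation table, so stratification may not work for that child.
- The baseline plaque score, one half of the change outcome, is taken once the arm is known to somebody. This third point applies on every route.

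**Working it through.** The plan gives no figure of its own on this point, so the first step compares the passages and the rest is illustrative arithmetic. The telephone share, examination-failure rate, dentition effect, outcome SD and examiner's knowledge of the arm are not documented. All are assumed below.

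**1. Order by route**

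| Route | First examination | Randomisation | Examination first? |
|---|---|---|---|
| In-person Visit 1 (Schedule of Events, body list) | Visit 1 | Visit 2 | Yes |
| Telephone Visit 1, then Study Summary Visit 2 | Visit 2, item 4 | Visit 2, item 3 | No |
| Visits combined | Same day | Same day | Not stated; only by inference |

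The Study Visits text alone could be met by an examination after allocation but before brushing. The conflict on the telephone route comes from reading it with Selection and Withdrawal of Subjects, where eligibility comes before study procedures.

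**2. Dentition imbalance**

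Inputs: the SAP's 2 primary, 27 mixed and 11 permanent (N = 40), with 20 per arm assumed.

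- If allocation ignores dentition for all children, the number K of permanent-dentition children in one arm is hypergeometric. Its mean is 5.5 and its variance is 20 × (11/40) × (29/40) × (20/39) = 2.045, so the SD is 1.430.
- The between-arm difference in share is (2K − 11)/20, with mean 0 and SD 2 × 1.430/20 = 0.143, or 14.3 points.
- Simulation (6,000 trials per setting, stratified blocks of 2 or 4 for the remaining children) gives an SD of about 4 points with full stratification, 8 if 25% are allocated before the examination, 10.6 at 50% and 13 at 75%. The mean is essentially zero throughout.

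Assume a within-dentition SD of 15 points in plaque reduction and a 10-point difference between permanent and other dentition. The SE with perfect balance is 15 × √(2/20) = 4.74. Adding imbalance gives √(4.74² + (share SD × 10)²):

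| Allocated before examination | SE | Against full stratification |
|---|---|---|
| 0% | √(22.5 + 0.40²) = 4.76 | – |
| 25% | √(22.5 + 0.80²) = 4.81 | +1.1% |
| 50% | √(22.5 + 1.06²) = 4.86 | +2.1% |
| 100% | √(22.5 + 1.43²) = 4.95 | +4.1% |

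At 100%, over SDs of 10 to 20 and dentition differences of 5 to 20 points, the rise against perfect balance runs from 0.6% to 34.8%. The top figure (SD 10, difference 20) is about 31% against full stratification.

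**3. Baseline score, only if the examiner knows the arm**

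The protocol's Background gives an average 42% reduction for manual brushes, so the post/pre ratio is 0.58. If one arm's baseline is scored 2%, 5% or 10% too high (assumed), the apparent reduction becomes:

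- 1 − 0.58/1.02 = 43.1% (+1.1 points)
- 1 − 0.58/1.05 = 44.8% (+2.8 points)
- 1 − 0.58/1.10 = 47.3% (+5.3 points)

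For scale, the Background's gap between powered and manual brushes is 46% − 42% = 4 points.

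**4. Exclusions after allocation**

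An assumed 5% to 15% is 2 to 6 of the SAP's 40 children or 3 to 9 of the planned 60. If they are not replaced, the SE rises by 1/√(1 − f) − 1, which is 2.6% to 8.5%.

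**The case against.** The strongest reply is that the body of the protocol already puts an examination first. With an in-person Visit 1, the examiner's evaluation is at Visit 1 and randomisation at Visit 2, so the Visit 2 evaluation reads as a repeat pre-brushing check. Combining visits does not delete the Visit 1 steps either. This stands for the in-person route. A reader might infer from the two Visit 2 lists that the plan breaks its eligibility rule for every child; the documents do not support that. The reply does not rescue the Study Summary's telephone route, and on a combined day it rests on inference.

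A second reply is that baseline plaque is not an entry criterion, so its place after allocation contradicts nothing. That is correct, and moving it is a design improvement. The Schedule of Events gives randomisation to research staff and plaque scoring to the examiner. The children see which brush they use, so the examiner is the natural blinded party. Exposure is therefore conditional.

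Third, the SAP describes how dentition was recorded for a secondary analysis. No passage names the source of the stratum used at allocation. This also stands: the plan leaves the source open, and does not show that stratification failed.

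A reader might also take the Risk and Benefit section, where the pre-use evaluation may end in a recommendation not to participate, as proof of exclusions after allocation on all routes. That section names no visit and sets no exclusion rule, and Withdrawal Criteria allows withdrawn subjects to be replaced. The most it supports is a possibility.

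**Conclusion.** The concern holds in limited form. For telephone-screened children the Study Summary's order conflicts with the eligibility sections and leaves no examined dentition status at allocation. For combined visits the order is unstated. For an in-person Visit 1 there is no eligibility conflict. Baseline scoring after allocation is a separate, avoidable weakness on every route.

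The size is modest. The expected dentition imbalance is zero, so the cost is precision: about 1% to 4% of the SE with an SD of 15 and a 10-point dentition difference. It reaches roughly a third only if every child is allocated before examination, the SD is small and the dentition difference is large. The planned unadjusted t-tests already carry such chance imbalance in their error. The baseline figures apply only if the examiner knew the arm. A reader might infer that children were in fact randomised before examination, or that the result is biased towards one brush; neither document shows either.

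**What to change.** Reconcile the Study Summary, the duration section and the body lists for Visits 1 and 2 with the Schedule of Events, Selection and Withdrawal of Subjects, Welcome Subject and Consent, and Study Visits. State one order for every route, including telephone screening and combined visits:

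1. consent;
2. eligibility examination and dentition classification;
3. pre-brushing plaque index and photographs;
4. randomisation within dentition stratum;
5. brushing.

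Say that the stratum comes from the examination in step 2. Scoring the baseline before allocation removes the question of examiner knowledge for that score, though not for the post-brushing score, so also state who is blinded.

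The cost is wording in the visit lists and a changed row order in the Schedule of Events. Existing steps are re-sequenced, with no added visit or procedure.

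If enrolment is complete, as the SAP's past tense suggests, report arm-by-dentition counts and post-allocation exclusions by arm. Where records allow, add the number of children randomised before their examination and whether the examiner knew the arm when scoring baseline plaque. The documents do not show that these last two items were recorded.

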## Background Information

A healthy mouth is a crucial condition for a healthy body.

Maintaining good oral health requires good oral hygiene meaning good plaque control. Plaque is one of the main etiological factors in dental decay and the principal etiologic factor for periodontal diseases which, beyond the discomfort they can inherently cause, are linked to more systemic conditions such as cardiovascular disease, pre-term low birthweight babies, Alzheimer's disease, and stroke.

It is now well recognized that tooth brushing is the most efficient plaque control method, at least when used in an optimal way.

Although toothbrushes have greatly evolved, from pig bristles to connected sonic devices, dexterity is still the key component to an efficient cleaning routine. Regardless of the type of toothbrush, if it cannot be used properly, plaque cannot be removed properly. And it has been shown in recent research that on a population with a general good health, the plaque score reduction is only an average 42% (range 30-53%) for manual toothbrushes and 46% (range 36-65%) for powered ones.

Based on these observations, the sponsor has developed a powered teeth cleaning device to bypass the variability of each individual dexterity according to which cleaning is performed by a contraction and a relaxation, according to successive cycles in the presence of a liquid dentifrice, of a mouthpiece made of a resilient material receiving and enclosing all the teeth of an arch.

---

[figure not shown]
## **Description of the Device Studied**

### **Device Classification**

Device is in class 1, 501K exempt according to the 21 CFR 872 section 6865.

### **Mechanism of Action**

The automated brush is a device aiming at improving and automating tooth brushing by bypassing the user's dexterity variability. To this end, it is composed of a combination of an injection pump and a vacuum pump that allows for the injection and the evacuation of a cleaning liquid into a supple TPE bristled mouthpiece enclosing one arch at a time. The border of the mouthpiece, the oral vestibule and the cheek create an airtight environment inside the mouthpiece, the suction of the liquid generates successive depressions allowing plaque disruption by the motion of the mouthpiece bristles onto the teeth surfaces.

Item	Designation	Material (if applicable)
#1	Body	ABS
#2	Hose	Food grade silicon
#3	Handpiece	TPU
#4	Mouthpiece connector	ABS
#5	Mouthpiece	TPE
#6	Anchor Waste	Food grade silicon
#7	Water tank	PC
#8	Liquid dentifrice cartridge	PET
#9	LED status indicator	ABS
#10	On/Off power button	ABS
#11	On/Off cycle button	TPU
#12	Cartridge connection	TPU
#13	Water connection	TPU

ABS: Acrylonitrile butadiene styrene

TPU: Thermoplastic elastomer

PET: Polyethylene terephthalate

---

## **Study Objectives and Purpose:**

Primary Objective: To compare the effects of the test brushing device versus a manual brush on plaque removal

Secondary Objective: To determine if soft tissue abrasion differs between test and control group

## **Study Design:**

This is 2 visit, single-blinded, randomized controlled clinical trial.

All subjects will sign an Institutional Review Board (IRB)-approved informed consent form before any study procedures may be performed. This study will be completed according to applicable Good Clinical Practices and the Declaration of Helsinki.

This study includes

### **Number of Subjects:**

The target number of subjects to be randomized to this study are 60 subjects.

### **Duration of subject participation and duration of study:**

All subjects will have two visits and should complete the study in approximately two weeks. The visits may be combined following a telephone screening. Each appointment will be approximately 90 minutes.

### **Schedule of Events:**

Procedures	Performed by:	Visit 1	Visit 2
Informed Consent	Research Staff	X	
Inclusion/Exclusion Criteria/Review	Research Staff	X	X
Enrollment	Research Staff	X	
Intra oral Examination	Examiner	X	
Randomization	Research Staff		X
Intra oral Examination (Pre & Post)	Examiner		X
Intra-oral photographs (Pre & Post)	Research Staff		X
Plaque disclosing index (Pre & Post)	Examiner		X
Brushing Dispense & Instruction	Research Staff		X

---

Study Product Usage	Subject		X
Schedule Next Study Visit	Research Staff	X	
Subject Compensation	Research Staff	X	X

### **Selection and Withdrawal of Subjects:**

Potential subjects will be recruited via flyers or direct contact at the Center for Pediatric Dentistry, with a phone number to call. A study staff will go over a checklist of the inclusion and exclusion criteria to determine if they are eligible to participate. At the initial visit a dental examiner will confirm the eligibility by the “yes” and “no” responses accordingly and ask additional questions as appropriate. Subjects who sign the informed consent form are screened for eligibility at the baseline visit. Subjects meeting all eligibility criteria shall begin the study procedures.

#### **Inclusion Criteria:**

- 5-17 years of age
- In good general health
- Fluent in English
- Willing and able to sign assent or informed consent as age appropriate
- Parent or guardian willing and able to provide written informed consent
- Be willing and able to carry out all study procedures (written and verbal) and be available at all times required for participation.
- 16 scoreable teeth (non-crown/bridge/ or full amalgams)
- Has had a dental exam and cleaning within 24 months

#### **Exclusion Criteria:**

- Advanced periodontal disease or severe gum disease
- Mouth or tooth pain that prevents brushing in any areas
- Have intraoral piercings (tongue or lip) that cannot be removed
- Have non-controlled diabetes
- Have any autoimmune or infectious disease or any medical condition that would delay wound healing
- Have untreated visible cavities or untreated dental work
- Had oral or gum surgery in the previous 2 months
- Take antibiotic premedication for dental procedures
- Undergoing or require extensive dental or orthodontic treatment, (space maintainers or removable appliances ok)
- Current smoker
- Generalized gingival recession over 1 mm

---

## **Withdrawal Criteria**

Study participation is voluntary. The subject may refuse to consent or may withdraw from this study at any time without penalty or loss of benefits to which he/she is otherwise entitled. The Principal Investigator may terminate a study subject's participation in this study without his/her consent (e.g., for safety or significant non-compliance) or other reasons that may warrant withdrawal.

The study team will document whether or not each subject completed the study. If, for any subject, study treatment or assessments were discontinued, the reason will be recorded.

Subjects that withdraw from the study may be replaced but their study ID will not be re used and no further subject's data will be collected after date of withdrawal.

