### **Product Use**

Subjects will be given verbal brushing instructions for the test or control brush.

For the control group, the toothbrush bristles will be dampened with water and toothpaste, will be pre-dispensed (on a clean surface) by the study staff to assure that all subjects are given the same quantity of toothpaste and to assure that the proper amount of toothpaste will be given. The same toothpaste will be provided to all the subjects. The subject will use the device directly over the sink.

Subjects will be reminded of the brushing instructions and will be timed during their brushing.

For the test group, the mouthpiece will be inserted by patient under the supervision of the study staff. The subject will use the device directly over the sink. If the subject is having any difficulty or uncomfortable, the in-mouth testing will be stopped immediately and reported to the Principal Investigator.

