Study title: Efficacy of a Novel Brushing Device

NCT #: NCT05038293

PI Name: [name]

Document Name: Statistical Analysis Plan

Approval Date: May 14, 2021

Please find the attached statistical analysis used for this study.

Statistical Analysis Plan

The proposed clinical study is a Single-blinded, randomized controlled clinical trial in humans designed to assess compare the effects the test brushing device versus a manual toothbrush.

Primary outcome analysis plan: Oral health status and plaque accumulation was measured and obtained through clinical examination. The Turesky modification of the Quigley-Hein Index was used to quantify the amount of dental plaque on six assigned index tooth sites in children (ages 5-17; N=40) prior to and after use of the assigned oral hygiene device. Individual tooth plaque scores were then averaged within device group pre and post brushing and reported (mean \pm sd). Data was assessed for normality using the *rnorm()* function within the “stats” package within R Statistical Software. Difference in mean plaque data within and between device groups pre and post brushing was then evaluated using the parametric *t.test()* function and adjusted for multiple testing by False Discovery Rate (FDR) with an *alpha* of 0.05 (95% CI) using the “rstatix” package within R Statistical Software.

Secondary outcome analysis plan: Dentition status (primary, mixed, permanent) was recorded through clinical examination. Data from the primary outcome (Plaque score using the Turesky modification of the Quigley-Hein Index) was then stratified to determine the impact of dentition status on outcomes between device groups. Individual tooth plaque scores were stratified by Dentition status (primary: N = 2; mixed: N = 27; permanent: N = 11) and then averaged within device group pre and post brushing and reported (mean \pm sd). Difference in mean plaque data within and between device groups and by dentition status pre and post brushing was then evaluated using the parametric *t.test()* function and adjusted for multiple testing by False Discovery Rate (FDR) with an *alpha* of 0.05 (95% CI) using the “rstatix” package within R Statistical Software.

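### Replacing children who withdraw after randomisation, alongside a stopping rule written only for the test arm, can tilt the primary comparison towards the device

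*Protocol*

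**What the plan says.** - **Order of events.** The protocol's Study Summary and Visit 2 list place randomisation before brushing. A child stopped while brushing is therefore already randomised.
- **Stopping.** Product Use deals with the arms in turn. The control instructions cover toothpaste and water and are followed by "Subjects will be reminded of the brushing instructions and will be timed during their brushing". The next paragraph opens "For the test group, the mouthpiece will be inserted by patient under the supervision of the study staff" and ends "If the subject is having any difficulty or uncomfortable, the in-mouth testing will be stopped immediately and reported to the Principal Investigator". No such sentence appears for the manual brush.
- **Withdrawal.** Under Withdrawal Criteria any child may withdraw at any time. The investigator may also end participation for safety, significant non-compliance or other reasons. Then "Subjects that withdraw from the study may be replaced", study IDs are not re-used, and "no further subject's data will be collected after date of withdrawal". Whether a child completed, and the reason for any discontinuation, are recorded.
- **Analysis.** The protocol's Statistical Analysis Plan section specifies a paired t-test on change within device and an unpaired t-test between devices. The SAP's primary outcome paragraph analyses plaque scores "prior to and after use of the assigned oral hygiene device". Neither text names an analysis set, says what happens when the post-brushing score is missing, or mentions stopped or replaced children.

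**The concern.** The post-brushing plaque index is due at the same visit as the brushing, soon after any stop. If a stop is treated as a withdrawal, the child would ordinarily leave without that score, and another child may take the place. The t-test cannot use a child with no post-brushing score.

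The children lost this way would be those who had trouble with the mouthpiece. An interrupted cleaning cycle plausibly removes less plaque, so their loss would raise the test-arm mean. The protocol presents the device as a way round differences in user dexterity, so children who cannot manage it bear directly on the claim. Replacement restores the headcount but not the randomised comparison, and it makes the loss harder to see.

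**Working it through.** **What can be reproduced.** The plan gives no stop, withdrawal or replacement rate. Its sample size of 60 (30 per arm) comes without effect size, SD, power or dropout allowance, so no stated figure can be checked. The arithmetic below only shows how sensitive the comparison is.

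**Inputs**
- Mean plaque reduction of 46% for powered and 42% for manual brushes (Background Information). These are literature averages for other brushes. Here they stand in for test-arm and control-arm completers.
- 30 children per arm (Study Overview).
- Assumed, not in the documents: *k* test children stopped and lost, each with plaque reduction *r*, and no control losses unless stated.

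**Step 1: break-even.** Let *f* be the fraction of test children lost. The completers-only test mean exceeds the all-randomised mean by *f* × (46 − *r*). This equals the 4-point gap when *f* = 4 / (46 − *r*).
- *r* = 0%: 4/46 = 8.7%, or 2.6 of 30
- *r* = 10%: 4/36 = 11.1%, or 3.3 of 30
- *r* = 20%: 4/26 = 15.4%, or 4.6 of 30
- *r* = 23% (half of 46): 4/23 = 17.4%, or 5.2 of 30
- *r* = 30%: 4/16 = 25%, or 7.5 of 30

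**Step 2: difference over all randomised children, *r* = 0%.** Completers alone show 46 − 42 = +4.0 points throughout.

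| Test children lost | No replacement: (30 − k) × 46/30 − 42 | Replaced to 30 completers: 30 × 46/(30 + k) − 42 |
|---|---|---|
| 1 | +2.5 | +2.5 |
| 2 | +0.9 | +1.1 |
| 3 | −0.6 | −0.2 |
| 6 | −5.2 | −3.7 |

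**Step 3: a false positive.** Suppose the true all-randomised difference is zero (both means 42%), and three test children with *r* = 0% are lost and replaced. The 30 completers then average 42 × 33/30 = 46.2, an apparent gain of 4.2 points. With standard error SD × √(2/30), the probability of a significant result favouring the device is 1 − Φ(1.96 − 4.2/SE). This is about 37%, 19% or 13% at assumed SDs of 10, 15 or 20 points, against a nominal 2.5% (two-sided 0.05, before any false-discovery adjustment).

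**Step 4: losses in both arms.** If a fraction *f*_C of control children is also lost, with the same *r*, the net overstatement is *f* × (46 − *r*) − *f*_C × (42 − *r*). With 10% lost in each arm and *r* = 0% it is 4.6 − 4.2 = 0.4 points. The bias therefore depends on losses being unequal between the arms.

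**The case against.** The strongest reply is that the step from stop to exclusion is nowhere written. Product Use says only that testing stops and the investigator is told. Withdrawal Criteria treat discontinuing treatment or assessments separately from withdrawing. The Schedule of Events and Visit 2 list include the post-brushing index with no exemption for a stopped child. Even the bar on further data applies after the date of withdrawal, so it does not literally forbid a score later the same day. All of this stands. The schedule, read alone, would have a stopped child scored. It does not settle the matter, because no text says that the schedule still applies after a stop or that a stop is not a withdrawal.

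A reader might infer that control children have no way out, so that the trial compares tolerant test children with all manual-brush children. The documents do not support this. Withdrawal, investigator termination and replacement apply to both arms, and Risk and Benefit Analysis asks every subject to report discomfort. Only the explicit stopping sentence is one-sided.

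A reader might also take the SAP's N=40, against 60 planned, as evidence that children were dropped this way. The documents do not explain the difference, so it shows nothing about this mechanism.

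The magnitude is also open to challenge. The 46% and 42% are not design values for this mouthpiece, and the stop rate and SDs are assumed. Zero removal may be too harsh, because the device cleans one arch at a time (Mechanism of Action) and a stopped child may have finished one. That is why the working shows a range of *r*.

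Finally, IDs are not re-used, discontinuation reasons and use errors are recorded, and reactions are counted by brushing method. These records would expose the losses. They would not bring the children into the efficacy comparison.

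**Conclusion.** The point holds as a conditional risk. The plan permits replacement after randomisation, ends data collection at withdrawal, places its only explicit stop in the test arm just before the primary outcome, and defines no analysis set. Together these can produce a selected comparison that favours the device. It would go too far to say that following the written rules must bias the result or that randomisation is undone, because no text makes a stopped child a withdrawal or leaves the child unscored.

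The size is unknown. In the illustration, about 3 of 30 test children lost with no plaque removal account for a 4-point gap, and about 5 of 30 if they achieve half the usual removal. Both figures assume the background averages, no control losses, and less plaque removal in stopped children than in completers. The point should be corrected because it touches the primary between-arm test and costs little, but it does not by itself invalidate the trial.

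**What to change.** Leave the clinical stopping rule as it is and change the analysis side:

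1. Restrict replacement to withdrawals before randomisation, or make replacements additional. Either way, every randomised child stays in the assigned arm for analysis.
2. State that the post-brushing plaque index already scheduled is still taken after a stop, where the child and family agree.
3. Where no post-brushing score exists, add a stated sensitivity analysis that sets the child's change to zero.
4. Report stops, withdrawals and replacements by arm.

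The SAP is written in the past tense with final counts, so data collection may already be complete. If so, item 2 can no longer recover scores. Items 3 and 4 and an accounting of all randomised children can still be done from the recorded discontinuation reasons. Separately, the sponsor should reconcile the stopping text between the two arms in Product Use; no clinical rule is suggested here.

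The cost is about one paragraph in each document. The one downside is that the test-arm estimate may be slightly less favourable.
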